## 4.0 Resources and Personnel

All data collection procedures for this study will be conducted at the VA Puget Sound in Seattle, WA.

The physical therapy will be performed at the gym located in building 103, Room 1106, or Room 510 (Building 1). The gait and balance testing will be done at the RR&D Center Motion Analysis Laboratory located in Building 100, Room 1D-118D, Room 510 (Building 1) or Physical Therapy Gym Building 103, Room 1106. Lastly, all interviews and neuropsychological evaluations will be performed in Room 130 at the Clinical Research Unit (CRU), Room 510 (Building 1), or Physical Therapy Gym Building 103, Room 1106.

Under the supervision of the PI: the research assistant will be responsible for conducting recruitment, screening, consenting and scheduling study procedures. The research assistant will also perform cognitive testing under the supervision of a neuropsychologist. Physical therapists will be in charge of gait training as well as gait analysis. The PI and co-investigator will be primarily responsible for data analysis and interpretation. (See more details about the Study personnel above (1.0))

We have also a collaborator in RR&D, [name], who will help with facilitating the use of the Motion Analysis Laboratory and data collection and analysis. The assessments however will be performed using our system, a portable APDM Movement Monitoring Solutions system (APDM, Inc.) which is more efficient for the measurements we will be collecting.

## 5.0 Study Procedures

### 5.1 Study Design

To achieve these aims we will enroll thru the WPDR 30 Veterans with PD (10 subjects in each the three genotype groups: (1) at least one BDNF-Met66 allele, (2) at least one APOE-ε4 allele and (3) no Met66 nor ε4 allele) in a 10-week moderate intensity gait training program consisting of 2 times per week treadmill training with verbal cues for gait quality. Genotypes will be available thru the WPDR and recruitment will be targeted for those groups of patients.

Aim 1 will examine the association between variants in 2 genes known to affect cognition and motor learning (APOE-ε4 and BDNF-Met66), and motor improvements after gait training. Aim 2

will examine the effect of APOE-ε4 and BDNF-Met66 genetic variants on cognitive changes in response to this training program.

Participation in this study involves a total of 22 visits to the VA Puget Sound (**Table 1**). These visits will occur over approximately 16 weeks, for a total of ~28 hrs.

In the rare event that we cannot meet our targeted number, we will contact and recruit non-Veterans also enrolled in WPDR.

**Visit 1**, the baseline assessment, will include:

- 1) An interview to collect key demographic variables (such as gender, age, height, weights, etc.) as well as information about the disease, medications, etc.
- 2) A visit with a neurologist to test the severity of PD motor signs using the Movement Disorders Society Unified Parkinson's Disease Rating Scale (MDS-UPDRS).
- 3) Questionnaire to assess fall history including the number of recent falls, circumstances, causes, and associated injuries
- 4) Questionnaire about physical activity levels using the International Physical Activity Questionnaire
- 5) A quick series of clinical tests of balance and gait including the Mini-Balance Evaluation Systems Test (mini-BEST), the 6-minute walk test, the Activity Specific Balance Scale Test, a Sensorimotor and Vision screen, and the Dynamic Gait Index (DGI).
- 6) A neuropsychological assessment using a brief, targeted battery of test including both paper and pencil and computerized measures. We will perform this in a quiet environment in the Clinical Research Unit (CRU) (room 130), Room 510 (Building 1), or building 103, room 1106, also at the VA Puget Sound Healthcare System.
- 7) A more quantitative balance and walking assessment using an APDM Movement Monitoring Solutions system (APDM, Inc.), which uses six inertial sensors attached to the wrists, feet, pelvis, and trunk to quantify body movements during mobility tasks. These tasks will include walking back and forth across a 7-m course for one minute. Two trials each will be performed under single-task (walking only) and dual-task walking (walking while performing serial-3 subtractions). We will do this at the VA RR&D Center Motion Analysis Laboratory (building 100, room 1D-118D at the VA Puget Sound, Room 510 (Building 1), or Physical Therapy Gym Building 103, Room 1106)
- 8) Additional questionnaires concerning sleep and quality of life including the Parkinson's disease sleep scale (PDSS-2), the Epworth Sleepiness Scale (ESS), and the Parkinson's disease questionnaire (PDQ-8).

This first visit will take approximately 4 hrs.

**Visits 1 through 20** will take place over 10 weeks, with 2 visits a week focused on a gait training program. Every patient will participate in the same rehabilitation program conducted at the physical therapy gym (building 103, room 1106 at the VA Puget Sound), or Room 510 (Building 1). Each training will take 1 hour. The program will involve two weeks of light intensity training on a treadmill with special focus on improving gait form, followed by 8 weeks of monitored, self-controlled moderate to vigorous intensity gait training on a treadmill, always using verbal cues for gait quality provided regularly throughout the gait training sessions.

**Visit 4** and **visit 20** will also include the same balance and walking assessments previously described in the baseline visit 1 (the mini-BEST, DGI, MDS-UPDRS, and the quantitative assessment), with **visit 20** also including neuropsychological assessments. Thus visit 4 will take an additional 1 hour while visit 20 will take an additional 2 hours.

**Visit 21** will take place approximately 6 weeks after you complete the rehabilitation program. This visit will only include the balance and walking assessments (again both the mini-BEST, DGI, MDS-UPDRS, and the quantitative assessment), for a 1 hour duration.

**Table 1. Summary of protocol for proposed research.**

	Pre-training (Baseline)	Start Training	Short-term Motor learning	Post-training	Follow-up (Retention)
Week	0	1	2	10	16
Gait training		weeks 1-10, 2x/week			
AIM 1: Gait assessment	X		X	X	X
AIM 2: Neuropsych. assessment	X			X	

### **Risks**

The potential risks of the proposed study are low, and this research is entirely non-invasive. Where potential risks have been identified, we have taken steps to mitigate them. Participants may find some of the questions in the baseline assessment (e.g., regarding medical comorbidities) are sensitive and may perceive this as an invasion of privacy. Participants will not be required to answer any questions that they do not choose to answer. For both Aims, participants will be asked to perform a variety of motor and cognitive tasks. During testing, participants may become fatigued. Participants will be able to rest as needed in order to complete tasks. Testing and gait training may result in some slight muscle soreness after walking. People with PD have a greater risk of falling than older adults without PD. We have taken great care to reduce the risk of falling. We will have 2 licensed physical therapists, and at least one will be present for all assessment and training sessions. All subjects will wear a gait belt and trained investigators will walk with them to guard against loss of balance and falls. Also, during gait training, a harness system for the treadmill will be available to reduce the risk of falls. We will monitor participants throughout the assessment and training sessions for any fatigue or soreness. Finally, because sessions will be 1-2 hours in length, water and a variety of snacks will be offered and available to participants throughout the sessions.

## **5.2 Recruitment Methods**

### **Recruitment.**

Recruitment will be done thru the Washington Parkinson Disease Registry (WPDR, MIRB#01023) using an Institutional Review Board (IRB) approved letter that describes the research study and provides contact information for the study. WPDR will contact Veterans that meet the requirements to participate in the study from an existing cohort of Veterans with PD who are already part of the registry. Potential participants will then contact the investigator of this project and will be screened by phone to determine their eligibility for this research. Eligible individuals will be scheduled for their baseline visit at a mutually agreeable time and will be sent a confirmation letter that includes a copy of the

informed consent document to review prior to study participation. The informed consent will detail the purpose, procedures, risks, and benefits of the research. Upon arrival in the laboratory for their baseline visit, the PI or appropriate study personnel will review the informed consent and answer any questions.

Results from the telephone screening will be kept in our database and shared with the WPDR to make further recruitment efforts for similar projects more efficient. For this purpose, we have filled out and submitted a request for waiver or alteration of the informed consent process form.

The WPDR will approach 60 individuals with the goal of recruiting a total 30 participants with PD, 10 subjects in each the following three groups: (1) at least one BDNF-Met66 allele, (2) at least one APOE-ε4 allele and (3) no Met66 nor ε4 allele. The genotypes will be available thru the WPDR and therefore will be used by WPDR during the recruitment to target those patients that fall in each of these three groups. In the rare event that we cannot meet our targeted number, we will contact and recruit non-Veterans also enrolled in WPDR.

### **Payment.**

Veterans will be offered compensation in return for the time and effort for a total of \$175: \$25 for the assessment at 2 weeks, \$50 for the assessment at 10 weeks and \$100 for the assessment 6 weeks after the program is done. Payments may be issued in cash or check (participant preference). We believe that the last assessment (6 weeks after the training finishes) is the most time consuming as participants are no longer coming to the VA for their training program and will just come here to do the assessment. The data from the last visit will help answering a very important question, which is the duration of the benefit provided by the training program. Thus we have assigned the last visit with the highest monetary compensation.

Checks will be mailed about 6-8 weeks after each visit, or cash payments can be collected through the agent cashier at the VA Puget Sound approximately 6-8 weeks after each visit.

### **5.3 Informed Consent Procedures**

The informed consent will detail the purpose, procedures, risks, and benefits of the research. Upon arrival in the laboratory, the PI or appropriate study personnel will review the informed consent and answer any questions. We will strive to ensure that all individuals understand the nature of the study. The decisional capacity of all prospective participants will be assessed by study personnel, in consultation with a study clinician, at the baseline visit. The assessment will be based on four key elements: the person's ability to 1) communicate a choice, 2) understand the relevant information, 3) appreciate a situation and its consequences, and 4) reason rationally, as described in detail in Appelbaum, N Engl J Med, 2007. Those individuals who are deemed to have impaired decisional capacity will not be enrolled in the study. Each individual will be told that they can choose not to participate in the study, that they can withdraw at any time, and that if they decide not to participate, it will in no way alter their medical care. Individuals who consent to participate in the study will be asked to sign the informed consent document

and will be given a copy of the signed form. All study personnel will complete the necessary human subjects' protections training per VA policy.

## 5.4 Inclusion/Exclusion Criteria

Patients will have to:

1. Meet UK Brain Bank (UKBB) criteria for the diagnosis of PD (modified so that having more than one affected relative was not considered an exclusion criteria);
2. Have a Hoehn & Yahr score of  $\leq 3$ .
3. Have the ability to walk 400 m without physical assistance from a device or another person.
4. Do not have other health conditions (e.g., orthopedic, cardiopulmonary) that impact the ability to safely participate in a moderately intense gait training program.

We will exclude those patients with a clinical diagnosis of dementia.

WPDR will first contact patients for recruitment that meet these inclusion criteria based on information recorded at their last visit in the WPDR database (UKBB criteria and Hoehn & Yahr are available for all patients). Once those patients interested in participating contact a staff member for this project, we will ask questions about their ability to walk and other health conditions during the phone screening. Finally eligibility will be determined after the patients perform the baseline visit where they will undergo a clinical and neuropsychological assessment by a neurologist and a neuropsychologist. At this visit we will make sure patients still meet UKBB criteria and Hoehn & Yahr requirements, as well as assess the ability to walk without physical assistance and their cognitive function. After the baseline evaluation, the neurologist and the neuropsychologist will review the results from all the assessments and generate a consensus clinical diagnosis of non-demented/demented and those diagnosed as demented will not be enrolled in this study.

## 5.5 Study Evaluations

**Demographics:** Sex, age, height, weight, ethnicity (incl. Hispanic origin), education, year of initial PD diagnosis, co-morbid medical diagnoses, and medications (PD & non-PD).

**Clinical characteristics & quality of life:** The severity of PD motor signs will be quantified using the Movement Disorders Society Unified Parkinson's Disease Rating Scale (MDS-UPDRS). Fall history will be assessed using a questionnaire including the number of recent falls, circumstances, causes, and associated injuries. Physical activity levels will be assessed using the International Physical Activity Questionnaire. Clinical tests of balance and gait will include the Mini-Balance Evaluation Systems Test (mini-BEST), the Activity specific balance confidence scale, a sensorimotor and vision screen, the 6-minute walk test, and the Dynamic Gait Index (DGI). Quality of life questionnaires will include the PDSS-2, PDQ-8, and the ESS.

**Gait Training Intervention:** All 30 individuals will attend a 10-week training program at the physical therapy gym at the VA Puget Sound, consisting of 1-hour sessions, twice a week (**Table 1**). The program will involve light intensity training on a treadmill with special focus on improving gait form for 2 weeks, followed by 8 weeks of monitored, self-controlled moderate to vigorous,

intensity gait training on a treadmill, with verbal cues for gait quality provided regularly throughout the gait training sessions. Adding verbal cues will incorporate declarative (explicit) in addition to procedural (implicit) learning processes. Feedback about the training speed achieved will be provided at the end of each 5-minute block.

**Balance and Walking Assessment: (AIM 1)** Walking will be assessed at the VA RR&D Center Motion Analysis Laboratory in a 1 hour session at 4 time points (**Table 1**): 0 weeks (baseline), 2 weeks (short-term motor learning changes), 10 weeks (long-term motor learning changes, immediately post-training), and 16 weeks (retention of motor learning, follow-up) using a wearable inertial sensor system. Motor learning will be assessed using gait speed during self-paced walking from baseline to 2 weeks (short-term motor learning changes) and from baseline to 10 weeks (long-term motor learning changes).

Objective spatiotemporal parameters of walking will be measured with the portable APDM Movement Monitoring Solutions system (APDM, Inc.), which uses six inertial sensors attached to the wrists, feet, pelvis, and trunk to quantify body movements during mobility tasks. We have used the APDM inertial sensor system extensively to quantify balance and gait in people with PD and other older adult populations, with data collection completed for >20 people with PD and >90 people with mild cognitive impairment or early AD. Participants will walk back and forth across a 7-m course for one minute. Two trials each will be performed under single-task (walking only) and dual-task walking (walking while performing serial-3 subtractions), allowing us to quantify changes in both straight-line walking and 180 degree turns under conditions of increasing cognitive load. Motor learning will be assessed using the primary outcome of gait speed during straight-line walking under single-task conditions. Therapists will be blinded to the subjects' genotyping status.

**Secondary analyses:** We will also measure retention and transfer of motor learning. Retention of motor learning will be assessed by differences in walking speed from post-training (10 weeks) to follow-up (16 weeks) time points (**Table 1**). Transfer of motor learning from a simple walking task (self-paced straight-line walking on a treadmill) to complex walking tasks (turning, dual-task walking) that are commonly impacted by PD will be assessed by the change in walking speed during complex walking tasks from pre-training to post-training time points.

Secondary walking measures to inform the mechanisms underlying any gait changes will assess specific gait domains (43-45) and will include step time, step time variability, step time asymmetry, and arm swing range of motion. These gait measures will be calculated in both single-task and dual-task walking conditions. In the dual task condition, performance of the serial-3 subtraction task will be audio recorded and the number of responses (correct and incorrect) will be tallied offline. Cognitive task performance will be measured as the correct response rate (number of correct responses per second), with number of correct responses and percent of correct responses (number of correct responses / total number of responses \* 100%). Turns will be quantified using peak turning velocity as the primary measure, with turn time and number of steps required to turn as secondary measures for turning.

**Neuropsychological Assessment: (AIM 2)** Cognitive performance will be measured at baseline (0 weeks) and post-training (10 weeks) (**Table 1**) using a brief, targeted battery aimed at assessing learning/memory, executive function, attention and processing speed. The battery will include both paper and pencil and computerized measures, and is approximately 45 minutes in length. When needed, we will minimize learning effects by using different versions of the same test pre- and post-training program. The battery includes:

- 1) **Story recall (46):** This measure of episodic verbal memory consists of an auditory presentation of a brief story, followed by immediate and delayed recall conditions.

Multiple validated equivalent versions of this measure are available and will be presented in a counterbalanced, randomized order.

- 2) Frontal Assessment Battery (47): This battery assesses a broad sampling of executive functions (abstract reasoning, phonemic verbal fluency, motor programming, interference, response inhibition) with minimal subject and time burden. It has been used in clinical trials and in pre- and post-intervention designs without apparent practice effects (48, 49).
- 3) Flanker Inhibitory Control and Attention Test (50): This computerized task is part of the NIH Toolbox and is derived from the Attention Network Test. It examines the participant's ability to inhibit visual attention to irrelevant stimuli.
- 4) Semantic verbal fluency (51): Semantic verbal fluency consists of asking the participant to produce as many words as possible in one minute that belong to a given semantic category.
- 5) Pattern Comparison Processing Speed Test (52): This computerized task from the NIH Toolbox measures choice reaction time by asking participants to quickly determine whether two visual stimuli are the same or different.
- 6) Dimensional Change Card Sort Test (50): The Dimensional Change Card Sort Test is a computerized measure of executive function/set shifting from the NIH Toolbox. A target is presented on the screen which must be matched to one of two choices, shape or color. During "switch" trials, the participant must quickly adapt to new rules for matching (e.g., first color, then shape, then color), with little feedback on how to do so.
- 7) Montreal Cognitive Assessment (MoCA) (53): The MoCA is a brief assessment of global cognitive abilities, including orientation, attention, memory, language, abstract reasoning, and visuospatial items. The MoCA has been shown to be a suitably accurate, brief test when screening for cognitive impairment in PD.

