
**SPECIFIC AIM 1: Determine the effect of genotype on motor learning in response to gait rehabilitation among Veterans with PD.** Aim 1 is designed to test the hypothesis that motor learning is reduced in those carrying *APOE-ε4* or *BDNF-Met66*. We will compare the effect of a 10-week gait treadmill-training program on motor learning, defined as increased walking speed from pre-training (0 weeks) to 2 weeks into training and to post-training (10 weeks), between the three genotype groups. Secondary hypotheses will determine the effect of genotype on: (1) the retention of motor learning changes (from post-training (10 weeks) to follow-up (16

weeks)); and (2) the transfer of motor learning from the trained walking task (straight line walking at a self-selected speed) to more complex walking tasks (dual-task walking and turning while walking) from pre-training to post-training..

**SPECIFIC AIM 2: Determine the effect of genotype on cognitive changes in response to gait rehabilitation among Veterans with PD.** We will compare the effect of a 10-week gait treadmill-training program on cognition in each of the three genotype groups. Changes in cognition will be assessed by comparing performance on cognitive tests from pre-training (0 weeks) to post-training (10 weeks).

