**Aim 2:** The primary hypothesis that those carrying *APOE* or *BDNF* genetic variants will experience reduced improvement in cognitive performance in different domains compared to those with *APOE-ε4* or *BDNF-Met66* genotypes, will be tested using a repeated-measures analysis of the covariance (ANCOVA), with visit (0 weeks, 10 weeks) as the within-group factor and genetic group (*BDNF-Met66* group, *APOE-ε4* group, no Met66 nor ε4 allele group) as the between-group factor for each of the tests, with adjustment for important covariates: age, disease duration and years of education.

All analyses will be performed using commercially available software (Stata, version 14.0; StataCorp).

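### Aim 2 attributes genotype differences in cognitive change to gait rehabilitation, but the design cannot separate training benefit from retest learning or natural course

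*Combined protocol and SAP*

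**What the plan says.** Section 3.0 (Specific Aim 2) sets the aim: "Determine the effect of genotype on cognitive changes in response to gait rehabilitation among Veterans with PD". Section 5.6 (Aim 2) gives the hypothesis that carriers "will experience reduced improvement in cognitive performance in different domains". It is tested separately for each test in a repeated-measures ANCOVA with visit (weeks 0 and 10) and genetic group as factors, adjusted for age, disease duration and years of education.

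All participants receive the intervention. Section 5.1 states: "Every patient will participate in the same rehabilitation program conducted at the physical therapy gym". Section 5.5 agrees: "All 30 individuals will attend a 10-week training program at the physical therapy gym at the VA Puget Sound". Table 1 places the neuropsychological assessment at weeks 0 and 10 only.

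On practice effects, the introduction to the battery in section 5.5 says: "When needed, we will minimize learning effects by using different versions of the same test pre- and post-training program". Two tests then get their own statement. Story recall has validated equivalent versions in counterbalanced, randomized order, and the Frontal Assessment Battery is described as free of apparent practice effects. Nothing test-specific is said for Flanker, semantic fluency, Pattern Comparison, Dimensional Change Card Sort or MoCA.

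**The concern.** Non-carriers are a comparator for genotype, not for training. Change from week 0 to week 10 in any group is the sum of training effect, gain from having taken the tests before, and natural course. The plan has no untrained group, repeat baseline or practice session to separate these, and the three planned covariates do not do so.

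In many designs this would matter little, because a practice gain common to all groups drops out of the group comparison. Here the variants were selected because they are postulated to affect learning (Abstract; section 3.0), and retest gain is a form of learning. If carriers gain less from re-exposure to the tests, the result points the same way as the hypothesis even if training does nothing for cognition. A genotype difference, real or not, could then be reported as a difference in rehabilitation response, which is the quantity that the programme wants for tailoring rehabilitation later.

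**Working it through.** **What the comparison identifies.** For genotype group g, write expected week 0–10 change as T(g) + R(g) + N(g): training, retest gain and natural course. The visit-by-group contrast between carriers (c) and non-carriers (0) estimates

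[T(c) − T(0)] + [R(c) − R(0)] + [N(c) − N(0)].

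Aim 2 names the first bracket. With everyone trained and two assessments, only the sum can be estimated. If R and N are equal across groups, the last two brackets are zero and the reading is correct.

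**Coverage of the battery.** Seven tests are listed. Removing story recall and the Frontal Assessment Battery leaves 7 − 2 = 5 that rely on the conditional general sentence alone.

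**Possible size.** The documents give no retest figures, alpha, SD or power, so there is no figure of theirs to reproduce. The following is illustration only. Assume two-sided alpha 0.05, SD of change 1, equal training benefit in all groups, and a retest gain smaller by b in both carrier groups.

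- If non-carriers gain 0.2 to 0.4 SD and carriers half that, b = 0.5 × 0.2 = 0.1 to 0.5 × 0.4 = 0.2.
- Group size 10 is from section 5.1. Error df = 30 − 3 groups − 3 covariates = 24.
- Group means (−b, −b, 0) have squared deviations summing to (2/3)b², so the noncentrality is 10 × (2/3)b² = 6.67b².
- The 2-df F test then rejects with probability 5.0% at b = 0, 5.4% at 0.1, 6.8% at 0.2, 9.2% at 0.3, 17.6% at 0.5 and 39.4% at 0.8.
- If 0.1 and 0.2 are instead SDs of the score, with an assumed retest correlation of 0.7, the SD of change is √(2 × 0.3) = 0.775. Then b becomes 0.13 and 0.26, and the rates are 5.7% and 8.1%.
- Pooling 20 carriers against 10 non-carriers (unadjusted t test), the chance of significance in the hypothesised direction is 2.5% at b = 0, 4.4% at 0.1, 7.2% at 0.2 and 23.8% at 0.5.

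**What an untrained comparator would cost.** Assume 80% power and the normal approximation.

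- Trained-only 1:1 comparison: n per group = 2[(1.96 + 0.842)/d]². At d = 0.8 this is 25, or 50 in total.
- Genotype-by-training contrast in four cells: n per cell = 4[(1.96 + 0.842)/d]². At d = 0.8 this is 50, or 200 in total, four times as many.
- Adding 30 untrained participants (20:10) to the planned 30 gives a minimum detectable difference of 2.802 × √[2(1/20 + 1/10)] = 1.53 SD. The trained-only contrast gives 2.802 × √(1/20 + 1/10) = 1.09 SD.

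**The case against.** The strongest defence has four parts.

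- **The safeguard covers the whole battery.** The sentence on different versions stands before the list of tests, so the plan recognises practice effects for all seven. The fluency item asks participants to "produce as many words as possible in one minute that belong to a given semantic category", which does not fix the same category at both visits. This stands. A reader might infer that five tests have no protection at all, but the documents do not support that. What those five lack is a test-specific commitment, because nothing says when the general one applies.
- **Differential retest gain is an inference.** The evidence in section 2.0 concerns motor learning and locomotor adaptation for BDNF, and motor decline, gait and poorer performance in some cognitive domains for APOE. None of it measures retest gain on tests such as these. This also stands: a smaller gain in carriers is plausible from the plan's premise, not established.
- **The artefact would seldom reach significance.** A reader might infer that weaker retest learning would by itself deliver a positive Aim 2. The figures above do not support that for modest differences at 10 per group. It would push estimates in the hypothesised direction without usually crossing the threshold.
- **This is a small first step.** Section 2.0 presents it that way and makes later tailoring conditional on subgroups being found. A single trained cohort is a legitimate choice at this size, and nothing in the plan changes rehabilitation on the basis of these 30 people.

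None of this rescues the attribution. The hypothesis in section 3.0 is worded partly in terms of timing (during or after training), but the specific aim that follows it still assigns the change to rehabilitation.

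**Conclusion.** The point holds as a limit on what Aim 2 can conclude. Followed exactly, the plan would attribute to gait rehabilitation a genotype difference that may include differential retest learning or natural course, and nothing in the design or model separates them. This follows from the design alone and needs no assumption about size.

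The direction (toward the hypothesis) rests on the assumption that carriers have the smaller retest gain. The size is unknown: zero if retest gain and natural course are equal across genotypes. Under the assumed 0.1 to 0.2 SD of change, per-test rejection rises from 5% to only 5.4 to 6.8%. The damage is to the meaning of the result more than to its error rate. The documents do not support a claim that the bias is present, that it would produce a positive trial, or that a control group is indispensable to a study of this scale.

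**What to change.** 1. State the Aim 2 objective and conclusion as a genotype difference in cognitive change over the 10-week training period, and say that this includes retest learning and natural course. Apply it wherever cognitive change is attributed to training: the Abstract (objectives and research design), section 3.0, section 5.1 and the Aim 2 paragraph of section 5.6. This is the essential change, because alternate versions reduce item-specific learning but not general familiarity with the task.
2. In section 5.5, replace the conditional sentence with a test-by-test commitment to different versions at weeks 0 and 10 wherever an equivalent version exists (for example, a different semantic category for fluency), in counterbalanced order. If the order is balanced by genotype, someone other than the cognitive tester should prepare the list. Section 5.5 blinds only the therapists, and section 4.0 has the research assistant doing the cognitive testing, so a genotype-coded list could reveal genotype to the tester.
3. Report tests without an alternate version as open to retest learning.

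The cost is protocol wording, a version schedule and a little care over who holds the list. No visit is added. Versions may differ slightly in difficulty, which counterbalancing spreads across visits, and the Aim 2 claim becomes more modest. An untrained comparator is not proposed, given the roughly fourfold sample size.
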